Historically, demodex blepharitis and MGD were treated together using mechanical treatment like warm compression and lid scrubbing and pharmacological treatment as Tea Tree Oil (TTO)(4). An FDA-approved solution for the disease is lotilaner ophthalmic solution, 0.25% (5), but its high cost at 1,957 USD per 10 ml is a notable drawback.

Hyun et al. (2012) found that only 7% of patients were Demodex-free after eyelid scrubs without the use of TTO. Therefore, in practice, we now recommend that patients with Demodex blepharitis treat their condition with eyelid scrubs containing TTO for higher treatment efficacy.(6)

Patients often find eyelid hygiene tedious and time-consuming, leading to poor treatment compliance (7). Recent innovations in in-office MGD management include Intense Pulsed Light (IPL), proposed as an adjunctive therapy for demodicosis. IPL's heat transfer may kill Demodex mites and soften meibum, reducing inflammatory mediators. Limitations include cost and inapplicability to patients with darker skin tones (Fitzpatrick V or VI), light-intolerant individuals, or pediatric patients (4).

An alternative cellular-level therapy overcoming IPL limitations is Low-Level Light Therapy (LLLT), using near-infrared light to induce mitochondrial light absorption and cell photoactivation, causing changes in inflammatory protein expression (8). This technology, recognized by NASA for

plant growth and astronaut wound healing (9), has diverse applications, including dermatology for Androgenetic Alopecia (AGA), skin rejuvenation, body contouring (10), and orthopedics for reducing edema, inflammation, and relieving pain and stiffness.

For direct effect to demodex mite Avci et al. (2013) and Sulek et al found that blue light activates porphyrins, leading to an antibacterial effect(11, 12). Rhee et al. (2023) conducted a comprehensive review revealing that Demodex mites can carry Streptococcus and Staphylococcus species on their surface, while *Bacillus oleronius* is present in their abdomen.(4)

Recently, LLLT has been used for MGD, with devices allowing combined (13) or separate (14) treatment with IPL or LLLT emerging as alternatives for MGD management.

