The lashed epilation technique lacks a standardized method. Numerous studies conducted from 1967 to 2024 have demonstrated that approximately 40% of these studies utilize the Modified Coston method as outlined by Gao et al. in 2005. In this method, two lashes containing cylindrical dandruff (CD) were extracted from each eyelid of every participant using fine forceps. These lashes were then individually placed at opposite ends of a glass slide for observation under a slit-lamp biomicroscope (SL220; Carl Zeiss, Oberkochen, Germany) at a magnification of $\times 25$. This process resulted in eight lashes (4 per each eye) being prepared across four slides for each participant. A coverslip was applied to each lash, followed by the slow pipetting of 20 μL of saline at the coverslip's edge until it surrounded the lash. Subsequently, 20 μL of 100% alcohol (Sigma-Aldrich, St. Louis, MO) was pipetted at the same edge, extending the counting period for up to 20 minutes to facilitate the migration of embedded Demodex from the CD. The Demodex count was performed thrice under the microscope, and all samples were photographed using standard procedures by the same specialist. The presence of Demodex in at least one of the eight eyelashes was considered Demodex-positive.(22)

Regarding epilation techniques, there are three primary methods:

- A) Direct pulling,
- B) Rotating the lash before epilation, and
- C) Removing the cylindrical dandruff from the base of the lash before epilation.

Bitton et al. in 2024 concluded that Technique B, involving rotating the lash before epilation, yielded the highest Demodex count. (23)

In our study, we intend to use Technique B along with the Modified Coston method for counting Demodex mites. These distinct parameters and methodologies contribute to the understanding of demodex blepharitis treatment, but a comprehensive investigation of LLLT in this context is notably absent in the existing literature.

4.4) Eyelid scrubb compliance

Hyun Koo et al. (2012) demonstrated that good compliance with eyelid scrubbing using tea tree oil (TTO) (defined as more than 10 times per week with over 70% compliance) resulted in significant improvements in both Demodex count and the Ocular Surface Disease Index (OSDI) scores. In contrast, the moderate and poor compliance groups did not show statistically significant improvements compared to the control group.(6)

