For our study, we will exclude patients with moderate and poor compliance. By focusing on patients who strictly adhere to the treatment protocol, we aim to more accurately assess the effectiveness of the intervention.

4.5) FDA approved medication for Demodex blepharitis : Lotilaner ophthalmic solution 0.25% is the only medication for Demodex blepharitis that was FDA-approved in July 2023(5). A recent meta-analysis showed that lotilaner significantly reduces Demodex mite density and mean collarette scores compared to a placebo(24). However, the cost per bottle is \$2,031 for 10 milliliters, and it is not available in Thailand. Consequently, we did not select this medication as an intervention in our study.

4.6) Several imaging modalities are used to diagnose MGD, with meibography emerging as a key tool for evaluating the structure and function of the meibomian glands. Traditional meibography employs infrared light to visualize gland architecture and assess gland dropout, but its reliance on manual interpretation can introduce subjectivity. The advent of artificial intelligence

(AI) in ophthalmology has opened new opportunities for more precise, automated, and objective assessments of meibomian gland health. AI-assisted meibography systems, particularly those based on deep learning algorithms, offer the potential to enhance the accuracy of MGD diagnosis and monitoring by providing automated segmentation, analysis, and grading of meibomian glands(25)

Recent studies have demonstrated the effectiveness of AI in analyzing meibography images to detect structural changes in the glands, including gland dropout and atrophy, with high sensitivity and specificity. [name] et al. described the use of deep learning models in meibography for the automatic segmentation of meibomian glands, offering a significant improvement over manual grading in terms of both speed and consistency. Their software integrates multiple steps, including image normalization, automatic segmentation, and manual refinement, to ensure high-quality analysis (18) By providing quantitative data on gland morphology, AI-based tools can assist clinicians in more accurately diagnosing MGD and tailoring treatment plans (26)

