Alternative Hypothesis (H1):

There is a significant difference in the reduction of Demodex mite count among patients with Demodex Blepharitis treated with at least one of the following therapies: Low Level Light Therapy (LLLT), Intense Pulse Light Therapy (IPL), Combined LLLT + IPL, greater than Mechanical with pharmacological Treatment.

[figure not shown]
Hypotheses

- LLLT or IPL, will be equally effective in reducing Demodex mite count and improving ocular surface parameters.
- IPL + LLLT will be more effective than LLLT or IPL alone in reducing Demodex mite count and improving ocular surface parameters.

7. Keywords

Demodex blepharitis, MGD, LLLT, IPL, Demodex mite count, Demodex mite eradication, Ocular surface parameters

Conceptual framework

Variables

Independent variables:

the different treatment modalities:

- 1.Low Level Light Therapy (LLLT)
- 2.Intense Pulse Light Therapy (IPL)
- 3.Combined LLLT + IPL
- 4.Mechanical with pharmacological treatment

Dependent variables: Mean Demodex Count, MGD Staging, OSDI Questionnaire, Meibum Quality, Meibum Expressibility, Telangiectasia Grading (0-3), Surface Staining (NEI Grading System), % Meibomian Gland Loss (MGL), Lipid Layer Thickness, Noninvasive Break-Up Time (NIBUT), Tear Meniscus Height (TMH),

8. Research Design

Single Center, 2x2 Factorial Randomized Control Trials

9. Research Methodology

Target Population: Demodex blepharitis patients at the Department of Ophthalmology, King Chulalongkorn Memorial Hospital.

This is a single-center, prospective, 2x2 factorial Randomized Control Trials involving outpatients with Demodex blepharitis presenting at the Department of Ophthalmology, King Chulalongkorn Memorial Hospital (KCMH) from Nov 2024 to Nov 2025.

The approach to participants: involves patients under the care of the research physician. They are recruited through advertisements and contacted through the patient's physician to introduce the researcher and seek volunteer participation.

The inclusion criteria consist of:

1. All patients who received a definite diagnosis of demodex blepharitis based on cylindrical dandruff at the base of the lashes and the presence of at least one alive demodex mites on eyelid margin by microscopy
2. Age >18 years.
3. Patients who can understand and follow the study instructions and can adhere to the scheduled follow-up plan.

The exclusion criteria consist of:

1. Patients who received previous treatment IPL or LLLT

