2. Poor compliance with eyelid scrubbing using tea tree oil (TTO)
3. Dead demodex mite on lash.
4. Contraindication of IPL: Skin Fitzpatrick scale V/VI, patients with pigmented lesions on the treatment area (Eyelid, Cheek).
5. Pregnancy or breastfeeding.
6. Active Skin disease: facial skin cancer, graft-versus-host disease, systemic lupus erythaematosus
7. Active eye infection: recurrent herpes simplex
8. Other lid disease ocular trauma, ocular deformity scar, exophthalmos, eyelid insufficiency
9. Patients with pigmented lesion on area of treatment.

We will use computer-generated random number allocation into 4 groups in a 1:1:1:1 ratio including seed number, with the outcome assessor blind and participant blind with allocation concealment:

- 1.) ShamLLLT + ShamIPL
- 2.) LLLT + ShamIPL
- 3.) IPL + ShamLLLT
- 4.) LLLT + IPL

***All groups receive mechanical with pharmacological treatment (Warm compression + Lid hygiene + 1% TTO) for 90 days with google form logbook for record compliance and prevent co-interventional treatments.

***All group with participant/investigator/interpreter blind.

Blinding and Allocation Concealment in Research Team:

1st Research Assistant : Allocates patients according to computer-generated random number allocation, ensuring allocation concealment, Evaluated VA , IOP , OSDI score by reads the questionnaire to the participant

2nd Research Assistant (The treatment administrator) : Administers IPL, LLLT, or sham treatments.

3rd Research Assistant : Conducts assessments using Keratograph and Lipiview2.

Main Researcher : Evaluates primary and secondary outcomes using case record forms, remaining blind to the treatment groups.

Intervention Description

Mechanical with pharmacological treatment : Warm compression 15 minutes + Lid hygiene + 1% TTO for 90 days

1%TTO : OCuSOFT Oust Demodex Eyelid Cleanser Foam Bottle 50ml (OCuSOFT, Richmond, TX) is the only commercially available medication in Thailand that contains 1% tea tree oil.

IPL : The Eye-light device (Espansione Marketing S.p.A., Bologna, Italy, waveleggths 1,200-1,500 nm, Delivery system 12cm²) (Thai FDA No 66-2-2-0012685) :

- Protective eye shields
- 5 flashes of light were applied for each eye (3 along the inferior orbital rim, 1 at the lateral canthus, and 1 applied horizontally along the inferior orbital rim)
- Therapeutic energy level (10–16 joules/ cm²) based on the degree of skin pigmentation.

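### Section 4.4 excludes moderate and poor scrub compliers, exclusion criterion 2 only poor ones; neither says when compliance is judged, and no analysis set is named to settle who is analysed

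*Combined protocol and SAP*

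**What the plan says.** Section 4.4, on eyelid scrub compliance, sits within the literature review but ends with a rule for this trial: "For our study, we will exclude patients with moderate and poor compliance". The reason follows: "By focusing on patients who strictly adhere to the treatment protocol, we aim to more accurately assess the effectiveness of the intervention".

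The operative list in Section 9 is narrower. Exclusion criterion 2 reads "Poor compliance with eyelid scrubbing using tea tree oil (TTO", with no threshold and no time point. Moderate compliance is not mentioned there.

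The only cut-off anywhere is the one Section 4.4 reports from a cited tea tree oil study, where good compliance was "defined as more than 10 times per week with over 70% compliance". The protocol does not adopt it expressly, and it does not separate moderate from poor.

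Compliance is recorded on study. Section 9 gives all four groups warm compresses, lid hygiene and 1% TTO "for 90 days with google form logbook for record compliance and prevent co-interventional treatments". Section 10 also mentions a paper logbook for the same purpose. Section 11 names no analysis set; it says only that unavailable data count as missing and are left out of calculations.

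**The concern.** Two people applying this plan could analyse different patients. One, working from Section 9, keeps moderate compliers; the other, working from Section 4.4, drops them. One judges compliance before entry; the other reads the logbooks afterwards.

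The second choice matters more. Scrubbing is background treatment in every arm and starts within the trial. If patients are removed for how well they scrubbed after allocation, the arms being compared are no longer those that randomisation produced. The protocol's own account makes scrub compliance prognostic: in the study cited in Section 4.4, good compliers improved on Demodex count, while moderate and poor compliers showed no significant improvement over control. Selecting on such a variable can unbalance the arms on the primary outcome if the selection works differently in them. Nothing in Section 11 prevents this, because no analysis of all randomised patients is stated.

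**Working it through.** No published figure is in dispute, so the check is mainly a comparison of the texts.

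1. **Who is excluded.** Good complier: kept under both rules. Poor complier: excluded under both. Moderate complier: excluded under Section 4.4, kept under criterion 2. The rules differ for one whole category, and that category has no definition.

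2. **When the rule applies.**
   - *For screening:* criterion 2 is in the eligibility list, among items normally checked at entry (previous IPL or LLLT, skin type, pregnancy).
   - *For on-study compliance:* the reason in Section 4.4 concerns adherence to the protocol treatment. The logbooks, kept during the trial, are the only compliance record described. The schedule in Section 10 has one visit 0–14 days before treatment and no scrub run-in. Section 9 recruits partly by advertisement and does not require previous TTO use, so some entrants may have no earlier scrubbing to judge.
   - Neither reading is ruled out.

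3. **Order of events on the on-study reading.** Scrubbing lasts 90 days. If it starts no earlier than the first visit (an assumption; the start is not stated), the longest interval to the week-8 visit is 14 + 8 × 7 = 70 days, which is less than 90. Compliance over the full period would therefore be known only after the primary count. The exact gap depends on start and count days that the protocol does not fix, so only the order is claimed.

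4. **Whether a size can be given.** In one arm, let f be the share excluded and d the mean count of retained minus excluded patients. Since mean(all) = (1 − f) × mean(retained) + f × mean(excluded), it follows that mean(retained) − mean(all) = f × d. The comparison of arms A and B therefore moves by fA × dA − fB × dB. The documents give none of these four quantities. The shift is zero when the two products are equal, for example when both f and d match; equal exclusion rates alone are not enough. The expression also does not separate selection bias from a treatment effect that truly differs by adherence. Neither size nor sign can be derived.

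5. **Analysis set.** Section 11 names neither an all-randomised nor a per-protocol population. Its one rule on omission concerns unavailable data. A poor or moderate complier with a week-8 count has available data, so that rule alone would keep the patient, while Section 4.4, applied on study, would not.

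**The case against.** The strongest reply is that this is a screening criterion, loosely echoed in a literature review. The binding list is in Section 9. Inclusion criterion 3 likewise selects people who "can adhere to the scheduled follow-up plan". Earlier scrubbing could be known for some: the background says "we now recommend that patients with Demodex blepharitis treat their condition with eyelid scrubs containing TTO", and the approach to participants "involves patients under the care of the research physician". The logbook is there to record compliance and discourage co-intervention; nowhere is it said to trigger removal. Section 14 lists imperfect adherence as a limitation, which fits better with such patients staying in the data. Sham procedures and participant blinding also make similar compliance across arms more likely.

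Much of this stands. A reader might infer that the plan commits to a per-protocol primary analysis or to dropping patients after randomisation. The documents do not support that: it is one reading of an ambiguous rule, and no per-protocol analysis is named.

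The reply does not remove the point. On a pure screening reading, Sections 4.4 and 9 still disagree about moderate compliers, the terms remain undefined, and no pre-entry assessment is described. Blinding reduces the risk of unequal selection but does not exclude it; Section 14 itself concedes that allocation is hard to conceal with light-based treatments.

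**Conclusion.** The point holds as an unresolved contradiction with a possible consequence for the primary comparison. Certain from the text: the two exclusion rules differ, timing and definitions are missing, and no analysis set is named. Conditional: if Section 4.4 is applied to on-study compliance, the week-8 comparison is conditioned on a post-allocation, prognostic variable, and full 90-day compliance would be settled after the primary count.

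A reader might want to attach a number of mites, or a loss of precision, to this. The documents give no compliance rates and no counts by compliance within arms, so any such figure would reflect invented inputs. The bias may be zero and may go either way.

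This should be fixed before the data are analysed. Confidence is medium, because the screening reading is a fair one.

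**What to change.** - Reconcile Section 4.4 with exclusion criterion 2. Confine any compliance exclusion to information known before allocation, and state its definition and how it is assessed.
- State in Section 11 that the primary analysis includes all randomised participants in their allocated arm, whatever their scrub compliance on study.
- Align this with the missing-data rule in Section 11: say how missing week-8 counts are handled, since leaving unavailable data out of every calculation does not by itself give an analysis of everyone randomised.
- Keep the good-compliance subset as a sensitivity analysis only. Fix its cut-off and its assessment period in advance, with the period ending no later than the count being analysed.

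The cost is mostly drafting, plus one real decision on the method for missing counts. No visits are added. The drawback is that including non-adherent patients may dilute the estimated effect; the sensitivity analysis lets the sponsor still report on adherent patients.

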Low-level light therapy (LLLT) and intense pulsed light (IPL) have gained traction as adjunctive treatments for MGD. Both therapies aim to improve meibomian gland function by reducing inflammation, improving glandular secretion, and decreasing Demodex mite counts Previous Studies suggest that combining LLLT and IPL with conventional therapies for MGD and blepharitis can lead to better clinical outcomes than monotherapy. However, limited research has evaluated the specific impact of these therapies on meibomian gland structure, especially when assessed using AI-assisted meibography

Our study aims to fill this gap by comparing pre- and post-treatment meibomian gland parameters in patients with Demodex blepharitis, using AI-assisted meibography to evaluate the effectiveness of LLLT, IPL, and combined treatments. By leveraging AI technology, this research intends to offer more objective and quantifiable insights into the impact of these treatments on meibomian gland health, which could ultimately improve patient outcomes in MGD management.

4.7) AI-Assisted Meibography Analysis: Our study plans to utilize an AI-assisted meibography developed system (18) to evaluate and compare the severity of meibomian gland dysfunction before and after low-level light therapy (LLLT) treatment for Demodex blepharitis. What sets this study apart is the integration of advanced AI-driven image analysis, specifically designed to assess the effectiveness of light-based therapies, which are playing an increasingly significant role in the treatment of meibomian gland dysfunction. This novel approach allows for precise, quantitative evaluation of treatment outcomes, offering a cutting-edge method to measure improvements in gland function.

5. Objectives

Study objectives to fulfill the knowledge gap

Primary objective:

To evaluate and compare the efficacy of mechanical with pharmacological treatment, LLLT, IPL and IPL + LLLT with Demodex Mite Count in MGD-related Demodex Blepharitis

Secondary objectives:

To evaluate and compare efficacy of mechanical with pharmacological treatment LLLT, IPL, IPL + LLLT for ocular surface parameters in MGD-related Demodex Blepharitis

6. Hypothesis

Null Hypothesis (H0):

There is no significant difference in the reduction of Demodex mite count among patients with Demodex Blepharitis treated with Low Level Light Therapy (LLLT), Intense Pulse Light Therapy (IPL), Combined LLLT + IPL, and Mechanical with pharmacological Treatment.

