2nd-5th visit	
 - 1st – 4th week : Treatment session 1 per week x 4 weeks - 8th week : 1 month after treatment (2nd Data correction+Epilation)
6th visit	- 16 th week : 3 months after treatment(3 rd Data correction+Epilation)

All data will be collected using Microsoft Excel version 16.65 (Microsoft Inc, USA) and analyzed using SPSS Statistics.

Informed consent process: The study includes an informed consent (Board consent) process that allows the use of research data for future studies without the need for additional consent. . Data will be collected after this process and recorded by the investigator in a manner that subjects cannot be identified

Log book:

Provide a paper logbook to all participants to record compliance and prevent any potential co-intervention by patients or caregivers.

11. Data Analysis and Statistics

Sampling technique and Sample size: N=22 in each arm by

1-Way ANOVA Pairwise, 2-Sided Equality

$$n = 2\left(\sigma \frac{z_{1-\frac{\alpha}{2\tau}} + z_{1-\beta}}{\mu_A - \mu_B}\right)^2$$

$$1 - \beta = \Phi(z - z_{1-\alpha/(2\tau)})_+ \Phi(-z - z_{1-\alpha/(2\tau)}), z = \frac{\mu_A - \mu_B}{\sigma \sqrt{\frac{2}{n}}}$$

$$n = 2 \left(3.56 \frac{z_{1-\frac{0.05}{2\tau}} + z_{1-\beta}}{3.18 - 1.59} \right)^2$$

$$1 - \beta = \Phi(z - z_{1-\alpha/(2\tau)})_+ \Phi(-z - z_{1-\alpha/(2\tau)}), z = \frac{3.18 - 1.59}{3.56 \sqrt{\frac{2}{n}}}$$

n = Sample size (per pair) = 36, Each arm = 18, 20% drop out = 21.6 = 22 per arm

Φ = the standard Normal distribution function

Φ^{-1} = the standard Normal quantile function

α = Type I error, Significance level = 5%

β = Type II error, Power (1 - β): 80%

τ = the number of comparisons to be made = 6

Relative difference (δ) = 50% (or 0.50) by our expert opinion of minimal clinical significant difference

From previous study(28)

Standard deviation (σ) = Assume an estimated value based on available data or literature (28) = 3.56

(SD Demodex count at baseline)

$\mu_A = 3.18$

$\mu_B = 1.59$

Statistical analysis, plan, and data management

Demographic and baseline clinical characteristics will be presented as percentages for categorical data and as mean with standard deviation or median with interquartile range (IQR) for continuous data.

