For outcome ,Continuous data : Meibomian gland area ratio, Meibomian gland length and width,Meibomian gland diameter deformation index ,Meibomian gland tortuosity index, Meibomian gland signal index should be analyzed using ANOVA, while binary outcomes and ordinal data Meibomian gland dysfunction staging (severity) should be assessed using the chi-square test.

Any unavailable data will be treated as missing and will not be included in any calculations. The report will specify the percentage of missing data in each category. Statistical significance will be determined by a p-value < 0.05.

12.Ethical Consideration

The submission of the research proposal to the Institutional Review Board on Human Research at the Faculty of Medicine, Chulalongkorn University marks a pivotal step in ensuring the ethical oversight and approval of the prospective Randomized Control Trial (RCT)

Respect for Person:

Informed Consent: The principle of respect for persons underscores the importance of obtaining informed consent. Ensuring that participants have a clear understanding of the study's purpose, procedures, potential risks, and benefits is crucial.

Researchers employ transparent and comprehensive communication in the informed consent process, elucidating the randomization process, details of each intervention, and the freedom to withdraw at any point without repercussions.

Researchers will provide comprehensive information to ensure that volunteers understand the research well and make independent decisions regarding participation, without coercion or undue influence. If volunteers have legal representatives or proxies, they will be the ones reviewing the informed consent document and providing witness signatures. Researchers will seek permission from the hospital director at Chulalongkorn Hospital and will anonymize data using codes without disclosing patients' names, surnames, or hospital identification numbers.

Beneficence/Non-maleficence:

Risk-Benefit Assessment: Ethical research necessitates a careful evaluation of potential benefits against risks. Researchers must strive to maximize the positive outcomes of the study while minimizing any harm to participants.

Continuous monitoring of the interventions for unexpected risks and a commitment to modify or halt the trial if harms outweigh benefits are imperative to uphold the principles of beneficence and non-maleficence.

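### Section 6 hypothesises that LLLT and IPL are equally effective, but the plan has only difference tests and no margin or confidence-interval rule that could support it

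*Combined protocol and SAP*

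**What the plan says.** Section 6 (Hypothesis) has two layers. The formal null opens "There is no significant difference in the reduction of Demodex mite count among patients with Demodex Blepharitis treated with Low Level Light Therapy (LLLT" and goes on to name the other three groups. The formal alternative is that at least one light therapy reduces the mite count more than mechanical with pharmacological treatment. Two directional statements follow. One is that "LLLT or IPL, will be equally effective in reducing Demodex mite count and improving ocular surface parameters"; the other is that the combination beats either therapy alone.

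Section 11 (Data Analysis and Statistics) sizes the trial for "1-Way ANOVA Pairwise, 2-Sided Equality" with six comparisons. Four arms have 4 × 3 / 2 = 6 pairs, so LLLT versus IPL is one of them. The effect to detect is described as "Relative difference (δ) = 50% (or 0.50) by our expert opinion of minimal clinical significant difference", entered as means of 3.18 and 1.59. The SD is 3.56, labelled as the SD of the Demodex count at baseline.

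The analysis text says that the listed AI meibography measures "should be analyzed using ANOVA, while binary outcomes and ordinal data Meibomian gland dysfunction staging (severity) should be assessed using the chi-square test", and then: "Statistical significance will be determined by a p-value < 0.05". It names no test for the Demodex count. For that outcome the only test named is the pairwise one in the sample-size calculation.

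No section gives an equivalence or non-inferiority margin, a two one-sided tests procedure, or a rule for interpreting a confidence interval.

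**The concern.** A test for a difference can give evidence that two treatments differ. When it is not significant, it does not give evidence that they are the same. A hypothesis of equal effectiveness needs a stated margin and an interval shown to lie inside it, and the plan has neither. The hypothesis is therefore written down with no planned analysis that bears on it.

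The comparison matters to readers. The background presents LLLT as an alternative that overcomes limitations of IPL, and section 13 expects clinicians to choose between treatments by relative efficacy. An unsupported statement that the two work equally well would be used in that choice, when the data might still allow a difference as large as the one the investigators call clinically important.

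**Working it through.** **Inputs, all from section 11.** SD 3.56 (baseline count); difference 3.18 − 1.59 = 1.59; two-sided alpha 5%; power 80%; six comparisons; 18 evaluable per arm, 22 with dropout.

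**The plan's own figure.** Its formula with its own inputs gives n = 2 × [3.56 × (2.638 + 0.842) / 1.59]² = 121.4, so 122 per arm. The stated 18 is not reproduced. That is a separate error, relevant here only because it worsens precision.

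**Precision of LLLT minus IPL**, using the error variance pooled over four arms:
- 18 per arm: SE = 3.56 × √(2/18) = 1.187; df = 68, t = 1.996; 95% half-width = 2.37.
- 22 per arm: SE = 3.56 × √(2/22) = 1.073; df = 84, t = 1.989; 95% half-width = 2.13.

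Both exceed 1.59, so an observed difference of exactly zero would leave ±1.59 inside the interval.

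**Dependence on the SD.** The documents give no SD for the week-8 count or for the reduction, so 3.56 is an assumption for the outcome analysed. The half-width is t × SD × √(2/n), that is 0.665 × SD at 18 per arm and 0.600 × SD at 22:

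| Assumed SD | Half-width, 18 per arm | Half-width, 22 per arm |
|---|---|---|
| 2.0 | 1.33 | 1.20 |
| 2.5 | 1.66 | 1.50 |
| 3.0 | 2.00 | 1.80 |
| 3.56 | 2.37 | 2.13 |

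The half-width falls below 1.59 when the SD is under 1.59 / 0.665 = 2.39 (18 per arm) or 1.59 / 0.600 = 2.65 (22 per arm).

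**How often the test would be non-significant**, with SD 3.56 and the plan's normal-theory power formula. At 18 per arm and a true difference of 1.59, z = 1.59 / 1.187 = 1.340. Unadjusted power is Φ(1.340 − 1.960) = 0.268, and with six comparisons Φ(1.340 − 2.638) = 0.097.

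| True difference | 18 per arm, unadjusted | 18 per arm, six comparisons | 22 per arm, unadjusted | 22 per arm, six comparisons |
|---|---|---|---|---|
| 0 | 95% | 99% | 95% | 99% |
| 1.59 | 73% | 90% | 68% | 88% |

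At 18 per arm, an unadjusted non-significant result is only 0.95 / 0.73 = 1.3 times as likely under true equality as under a difference of 1.59. It says almost nothing about which holds.

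**Whether the factorial layout helps.** It does not. The LLLT main effect is ½[(LLLT − control) + (both − IPL)] and the IPL main effect is ½[(IPL − control) + (both − LLLT)]. Subtracting leaves LLLT − IPL, the simple contrast between two single arms.

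**The case against.** The strongest reply is that the documents never say a non-significant p-value will be read as equality. The significance sentence is silent on how a non-significant result is interpreted, the objectives are to evaluate and compare, and the formal hypotheses concern differences. The bullet may be only an informal expectation. This stands in part. A reader might infer that the plan would confirm the hypothesis by default, but no sentence sets such a rule. What remains is that the bullet is listed among the hypotheses and no planned analysis could support it.

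Second, ANOVA and chi-square are attached to the AI meibography outcomes, not to the mite count. That is correct. The test named for the mite count, in the sample-size calculation, is also a difference test, so the conclusion does not change.

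Third, the figures rest on a baseline SD. That stands, and the statement that a zero difference could not exclude 1.59 must carry its condition: it fails below an SD of about 2.39 or 2.65. A smaller SD narrows the interval; it does not turn p > 0.05 into evidence of equality.

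Fourth, much of the imprecision belongs to the sample-size error. At 122 per arm the half-width would be about 1.965 × 3.56 × √(2/122) = 0.90. That also stands. But even then any support would come from an interval read against a justified margin, not from a non-significant p-value.

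Finally, a reader might infer that 1.59 can serve as a ready-made equivalence margin. The documents do not support that. It is the whole effect the trial is sized to detect, so a therapy with almost none of the added benefit could be called equal to one with almost all of it. It is also in mites and says nothing about the ocular surface parameters in the same bullet.

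**Conclusion.** The concern holds as a mismatch between a stated hypothesis and the planned inference. The plan hypothesises equal effectiveness of LLLT and IPL on mite count and ocular surface parameters, and contains nothing that could support it. It does not follow that the investigators intend to read non-significance as equality.

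The numerical size applies to the mite count only and assumes that SD 3.56 carries over to week 8. On that assumption the interval is wider than the plan's minimal important difference at either arm size, and a true difference of that size would usually be missed. Part of that size comes from the separate sample-size error. The mismatch itself depends on neither the SD nor the number of patients. It should be corrected because it affects what the trial may conclude about a listed hypothesis on its primary outcome, although the formal null and alternative are untouched.

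**What to change.** Replace the bullet in section 6 with wording such as:

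> The difference between LLLT and IPL in Demodex count and in each ocular surface parameter will be estimated with a 95% confidence interval; a non-significant result will not be reported as equal effectiveness.

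Repeat the second clause in the statistical analysis text of section 11, next to the significance rule.

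Do not add a clause allowing an equality statement when the interval lies within ±1.59. Any equivalence claim would need a separately justified, pre-specified margin for each outcome, and a new sample size. For illustration only, two one-sided tests at 5% each, true difference zero, 80% power and SD 3.56 need 2 × [3.56 × (1.645 + 1.282) / margin]² per arm. That is 86 evaluable at an assumed margin of 1.59 and 344 at half of it. At margin 1.59 the figure falls to 61, 43 or 28 if the SD is 3.0, 2.5 or 2.0.

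The recommended change is rewording, with no effect on design, recruitment or procedures. Its cost is giving up an equality claim that the trial is very unlikely to be able to support.
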